^aThe screening period may be extended if additional time is needed to complete screening procedures, upon discussion with and approval by the medical monitor.^bEligible subjects will check-in either on Day -1 or Day 1, based on the investigator's decision.^cA follow-up telephone call will be performed 7 (+ 2) days after dosing to assess AEs and record concomitant medications.^dDay 1 predose assessments will be performed only for those subjects who check-in on Day 1 (ie, subjects who check-in on Day -1 will have their predose assessments on Day -1).^eSubjects may be released from the clinic after PK sample collection at 12 hours postdose to return the following morning or may remain in the clinic until 24 hours postdose, based on the investigator's decision. Subjects released on Day 1 will return to the clinic on Day 2 between 22 to 26 hours postdose for an outpatient visit, which will include EoT assessments and one PK sample. In-clinic subjects may leave the clinic on Day 2 after the EoT assessments and PK sampling are complete.^fVital signs will be assessed for all subjects at check-in, predose (within 2 hours before dosing) on Day 1, and 3 hours postdose on Day 1.

[figure not shown]
Protocol 405-201-00037

2 Introduction

Attention-deficit hyperactivity disorder (ADHD) is typically viewed as a childhood/adolescent disorder.¹ ADHD frequently begins between 2 and 4 years of age^{2,3} and it is most commonly diagnosed between 7 and 10 years of age. The diagnosis and treatment of ADHD of a very young child represents a diagnostic challenge.⁴ Because inattention, impulsivity, and hyperactivity can all be normal behaviors for a young child, making a diagnosis of ADHD often requires the degree and impairment of these symptoms to be beyond what is developmentally appropriate.⁵

It is widely believed that the core symptoms in ADHD result from dysregulation in the balance of 2 neurotransmitter systems in the prefrontal cortex, ie, norepinephrine (noradrenaline) and dopamine.^{6,7,8}

Centanafadine (EB-1020), which is an inhibitor of the uptake of norepinephrine, dopamine, and serotonin (5-hydroxytryptamine) in vitro and in vivo, is a novel drug candidate that is being developed as a treatment for ADHD in adults (≥ 18 years) and in children (4 to 17 years, inclusive).

Protocol 405-201-00037

Please refer to the centanafadine Investigator's Brochure (IB) for more detailed information.⁹

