4.2 Scientific Rationale for Trial Design

A single dose is expected to be predictive of multiple dosing; therefore, this trial will evaluate a single dose of centanafadine. The focus is on the evaluation of the centanafadine concentration-time profile through 12 hours postdose and measuring centanafadine concentrations at 24 hours postdose to determine the potential for accumulation following multiple doses; therefore, PK sampling through 24 hours is sufficient.

Protocol 405-201-00037

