8.2.1 Pharmacokinetic Blood Samples

Blood samples (4 mL, dipotassium ethylenediaminetetraacetic acid [K₂EDTA]) will be collected on Day 1 (1, 2, 3, 4, 6, 8, 10 and 12 hours postdose) and on Day 2 (one PK sample between 22 to 26 hours postdose), and will be processed into plasma for the determination of centanafadine, EB-10601, [REDACTED]

The actual date and time of the PK sample collection will be recorded in the eCRF. When vital signs or ECGs are scheduled at the same nominal time as PK sample collections, vital signs should be measured and ECGs should be performed before PK samples are collected.

After processing into plasma, aliquots will be placed into appropriately labeled tubes and will be placed in a freezer set at -70°C , unless otherwise instructed in the Operations/Laboratory Manual.

All plasma samples will be shipped to the bioanalytical laboratory for analysis. Additional information will be provided in the Operations/Laboratory Manual.

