This statistical analysis plan (SAP) documents the statistical methodology and data analysis algorithms and conventions to be applied for the analysis of clinical trial data of trial 405-201-00037 for centanafadine. The current version of SAP is based on protocol version 3.0 dated on 23 Jul 2019 and final SAP will be consistent with the final version of the protocol.

2 Trial Objectives

Primary Objectives:

To characterize the single-dose concentration-time profile from 0 to 12 hours of centanafadine in pediatric subjects (9 to 12 years, inclusive) with attention-deficit hyperactivity disorder (ADHD).

Other Objectives:

- To assess the safety and tolerability of centanafadine XR in pediatric subjects.
- To assess the ability of pediatric subjects to swallow the centanafadine XR capsule.
- [REDACTED]
- [REDACTED]
- To assess centanafadine concentrations 24 hours postdose for evaluation of the potential for accumulation following multiple doses.
- To compare the PK of centanafadine after administration of the intact capsules or the capsule contents sprinkled on to applesauce.

3 Trial Design

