3.1 Type/Design of Trial

This is a pilot phase 2a, multicenter, open-label, single-dose trial in pediatric subjects (9 to 12 years, inclusive) with a documented history of ADHD and confirmation of an ADHD prescription medication. This trial consists of a screening period (Day -21 to Day -2), check-in (Day -1 or Day 1), 2-day treatment period (Day 1: dosing, Day 2: end of-treatment [EoT]), and a safety follow-up telephone call 7 (+ 2) days after dosing (Day 8). The screening period may be extended if additional time is needed to complete screening procedures, upon discussion with and approval by the medical monitor.

Written informed consent will be freely obtained from all subjects' guardian(s) or legally acceptable representative(s), as applicable for local laws. Written informed assent will be freely obtained from all subjects.

Protocol 405-201-00037

Eligible subjects will check-in either on Day -1 or Day 1, based on the investigator's decision. A single dose of centanafadine will be administered either as intact capsules or the capsule contents sprinkled on a tablespoon of applesauce on Day 1 in the morning.

[figure not shown]
[REDACTED] Pharmacokinetic

and safety assessments will be performed for approximately 24 hours postdose. Subjects may be released from the clinic after PK sample collection at 12 hours postdose to return the following morning or may remain in the clinic until 24 hours postdose, based on the investigator's decision. Subjects released on Day 1 will return to the clinic on Day 2 between 22 to 26 hours postdose for an outpatient visit, which will include EoT assessments and one PK sample. In-clinic subjects may leave the clinic on Day 2 after EoT assessments and PK sampling are complete.

Subjects and/or their caregivers will be contacted by telephone 7 days after dosing to assess any new or ongoing AEs and to record concomitant medications.

The trial design schematic is displayed in [Figure 3.1-1](#).

Figure 3.1-1 Trial Design Schematic

ET = early termination; EoT = end of treatment.

^a The screening period may be extended if additional time is needed to complete screening procedures, upon discussion with and approval by the medical monitor.

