7.6 Protocol Deviations

Any major protocol deviation will be recorded in the eCRF along with the start date and details of the deviation. A subject listing will be provided describing the deviation date and reason for each subject.

8 Pharmacokinetic Analysis

A noncompartmental analysis will be performed. Plasma concentrations of centanafadine and metabolite(s) will be summarized by time point and mode of administration (intact capsules or capsule contents sprinkled on a tablespoon of applesauce). The PK parameters will be summarized by analyte and mode of administration using descriptive statistics.

No inferential statistical analysis will be conducted.

The following PK parameters will be summarized:

- Maximum (peak) plasma concentration (C_{max}) of centanafadine
- Time to maximum concentration (t_{max}) of centanafadine
- Area under the concentration-time curve from time 0 to 12 hours postdose (AUC_{0-12h}) of centanafadine
- Centanafadine concentration at 24 hours postdose

A large rectangular area of the page is completely blacked out, indicating redacted content. It spans from approximately [171, 670] to [870, 890].

Protocol 405-201-00037

10 Safety Analyses

All the following safety analyses will be performed for the safety sample.

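### Does drawing the 24-hour sample anywhere from 22 to 26 hours undermine the accumulation assessment?

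*SAP*

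**What the plan says.** SAP Section 2 includes the objective "To assess centanafadine concentrations 24 hours postdose for evaluation of the potential for accumulation following multiple doses". Protocol Section 4.2 gives the same reason for sampling that late. SAP Section 6.3 carries the 24-hour concentration as an endpoint, and SAP Section 8 lists it as a summarised parameter: "Centanafadine concentration at 24 hours postdose". Section 8 summarises concentrations by time point and by mode of administration, descriptively and without inference. SAP Section 2 has a second relevant objective: "To compare the PK of centanafadine after administration of the intact capsules or the capsule contents sprinkled on to applesauce".

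Protocol Section 8.2.1 schedules eight samples on Day 1, from 1 to 12 hours, and a single Day 2 sample between 22 and 26 hours. Footnote e of the Schedule of Assessments (Protocol Section 1.3) explains the window: "Subjects released on Day 1 will return to the clinic on Day 2 between 22 to 26 hours postdose for an outpatient visit". Others, in the words of SAP Section 3.1, "or may remain in the clinic until 24 hours postdose"; the investigator decides which.

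On timing, Protocol Section 8.2.1 says: "The actual date and time of the PK sample collection will be recorded in the eCRF". Protocol Section 6.4 and SAP Section 7.4 record the dose time as well.

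**The concern.** The label names one time and the sample may be taken over four hours. If concentration is still falling on Day 2, an early draw reads high and a late draw reads low. A summary by nominal time would then mix values that are not on the same footing. The visible text does not say whether nominal or actual time governs, and the missing-data rules in Protocol Section 9.3 and SAP Section 5.4 do not mention timing.

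Two uses could suffer. The accumulation judgement rests on this one value. The comparison of intact capsules with sprinkled contents could be distorted if one group were drawn systematically earlier, with only about six subjects per mode if 12 are treated. The times are already recorded, so a correction looks nearly free.

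**Working it through.** **Inputs.** From the documents: nominal time 24 h; window 22 to 26 h; up to 12 subjects, about half per mode (SAP Sections 3.2 and 4); no inferential analysis. The plan states no half-life, accumulation figure or power calculation, so there is no figure of its own to reproduce. Assumed: log-linear decline, half-life h of 4, 6, 8 or 12 hours, and a 50% between-subject coefficient of variation (CV).

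**Step 1: error in one subject's value.** At 22 h the error is 2^(2/h) − 1; at 26 h it is 2^(−2/h) − 1.

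**Step 2: error in the accumulation ratio.** Let f be the fraction remaining after one 24-hour interval, 2^(−24/h). The once-daily ratio is R = 1/(1 − f). Reading a 22-hour sample as a 24-hour one replaces f with 2^(−22/h). For h = 4, f goes from 0.0156 to 0.0221, so R goes from 1/0.9844 = 1.016 to 1/0.9779 = 1.023. For h = 12, f goes from 0.2500 to 0.2806, so R goes from 1.333 to 1.390.

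**Step 3: bias in the mean with draws spread evenly over the window.** With λ = ln 2/h, this is sinh(2λ)/(2λ) − 1.

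| Half-life (h) | One subject at 22 h | One subject at 26 h | True R | R if all drawn at 22 h | Change in R | Mean bias, even draws |
|---|---|---|---|---|---|---|
| 4 | +41% | −29% | 1.016 | 1.023 | +0.7% | +2.0% |
| 6 | +26% | −21% | 1.067 | 1.085 | +1.8% | +0.9% |
| 8 | +19% | −16% | 1.143 | 1.175 | +2.8% | +0.5% |
| 12 | +12% | −11% | 1.333 | 1.390 | +4.3% | +0.2% |

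The concentration error is large only where almost nothing accumulates. The change in R grows with half-life but is bounded: as h increases without limit, (1 − 2^(−24/h))/(1 − 2^(−22/h)) approaches 24/22 = 1.091. Even the extreme case of every draw at 22 h therefore cannot inflate R by more than 9.1% in this model.

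**Step 4: the comparison of modes.** If one mode were drawn on average d hours earlier, the spurious ratio would be 2^(d/h). For d = 1 this is 1.19 / 1.12 / 1.09 / 1.06 at the four half-lives; for d = 2 it is 1.41 / 1.26 / 1.19 / 1.12. Against that, a 50% CV gives a log-scale SD of √ln(1.25) = 0.472. With six per mode the standard error is 0.472 × √(2/6) = 0.273. The 95% half-width, with t = 2.228 on 10 degrees of freedom, is 0.608, which is a factor of exp(0.608) = 1.84 either way. Every figure for d = 1 or 2 lies inside that.

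**The case for a change.** The strongest reply is that the step is cheap and that small error in R does not cover the mode comparison. Mode follows a swallow test, not randomisation. Release from clinic is the investigator's choice. With about three sites and six subjects per mode, site, draw time and mode could become entangled by chance. Noncompartmental analysis on actual times, which the visible text does not promise, would still not turn a 22-hour value into a 24-hour one. A time-adjusted value, using each subject's decline over the 10-hour, 12-hour and Day 2 samples, did better in simulation: log-scale root mean squared error fell from 0.23 to 0.10–0.12 at a 4-hour half-life, and from 0.12 to 0.10–0.11 at 12 hours.

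Some of this stands. The visible text is silent on nominal versus actual time, and a sentence would make it clearer. The rest carries less weight. Chance imbalance is possible, but nothing in the documents ties mode to release or draw time, and the outpatient window is centred on the same 24 hours that in-clinic subjects stay to. The adjusted value also has a cost. It puts a three-point slope on an extended-release product, and it helps most at short half-lives. There, concentration at 24 h is down to 2^(−12/4) = 12.5% of its 12-hour level, so values below quantitation are likeliest. Those could not be adjusted, leaving a summary of mixed values. The simulation assumed 10% assay error and included no quantitation limit, so its gain is probably flattering.

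**Conclusion.** No change to the plan follows. The 24-hour label is the nominal centre of a window that both documents disclose, and recorded dose and draw times let any reader recover elapsed time. A pharmacokinetic analyst would list those times as a matter of course, and the blacked-out SAP text may already require it; text hidden by redaction cannot be counted as missing.

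Followed as written, the plan still supports a sound statement on accumulation. The ratio shifts by at most 4.3% across half-lives of 4 to 12 hours even if every subject is drawn at the early edge, and mean concentration is biased by 2.0% or less with even draws. Between-mode distortion needs a systematic timing difference that no document suggests, in a descriptive comparison uncertain by a factor of about 1.84. Cmax, tmax and AUC0-12h should be unaffected: AUC0-12h uses only Day 1 samples, and the peak is expected among them.

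These sizes rest on assumed log-linear decline, the assumed half-lives and an assumed 50% CV. A modelled 24-hour value is a debatable trade-off that would alter no conclusion.

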10.1 Extent of Exposure

A table displaying the number of subjects who took 1 day of study medication will be presented by mode of administration (intact capsules or capsule contents sprinkled on a tablespoon of applesauce). The summary will be based on the Safety analysis Set.

10.2 Adverse Events

All treatment-emergent adverse events (TEAEs) will be coded by Medical Dictionary for Regulatory Activities (MedDRA; Version 21 or later) system organ class and preferred term. Treatment-emergent adverse events are defined as those AEs that occur after administration of IMP or events that worsen relative to baseline.

Newly acquired skin eruptions that are nontraumatic will be considered AEs of special interest (AESIs). These may include but are not limited to eruptions such as skin rashes, skin irritations, skin reactions, or acneiform lesions. This does not include localized contact irritation at ECG lead sites due to application/removal of lead adhesive. Preferred terms from AE database will be reviewed by Otsuka medical team to determine the list to be included in AESIs table.

The incidence of the following events will be summarized:

- TEAEs
- TEAEs by severity
- TEAEs potentially causally related to the IMP
- TEAEs with an outcome of death
- Serious TEAEs
- TEAEs leading to discontinuation of study
- AESIs.

All TEAEs will be presented in a listing. The listing of death due to AEs, serious AEs, AEs leading to discontinuation, and AESIs will also be provided.

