8.8 Adverse Events

8.8.1 Definitions

An AE is defined as any untoward medical occurrence in a clinical trial subject administered an IMP and which does not necessarily have a causal relationship with this treatment. Adverse events would not include information recorded as medical history at screening for pre-planned procedures for which the underlying condition was known and no worsening occurred. An adverse reaction is any untoward and unintended response to an IMP related to any dose administered.

A suspected adverse reaction is any AE for which there is a reasonable possibility that the IMP caused the AE. For the purpose of Investigational New Drug (IND) safety reporting, "reasonable possibility" means there is evidence to suggest a causal relationship between the IMP and the AE. Suspected adverse reaction implies a lesser degree of certainty about causality.

Treatment-emergent AEs (TEAEs) are defined as AEs with an onset date on or after the start of open-label treatment. In more detail, TEAEs are all AEs that started after the start of open-label IMP treatment; or if the event was continuous from baseline and was worsening, serious, IMP related, or resulted in death or discontinuation from the trial.

Protocol 405-201-00037

An SAE includes any event that results in any of the following outcomes:

- Death
- Life-threatening; ie, the subject was, in the opinion of the investigator, at immediate risk of death from the event as it occurred. It does not include an event that, had it occurred in a more severe form, might have caused death.
- Persistent or significant incapacity/disability or substantial disruption of the ability to conduct normal life functions.
- Requires inpatient hospitalization or prolongs hospitalization.
 - Hospitalization itself should not be reported as an SAE; whenever possible the reason for the hospitalization should be reported.
 - Hospitalizations or prolonged hospitalizations for social admissions (ie, those required for reasons of convenience or other nonmedical need) are not considered SAEs.
 - Prescheduled hospitalization to address a condition that has existed prior to the signing of the ICF and assent form should not be considered an SAE.
- Congenital anomaly/birth defect.

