8.8.2 Eliciting and Reporting Adverse Events

The investigator will regularly assess subjects for the occurrence of AEs. To avoid bias in eliciting AEs, subjects should be asked the nonleading question: "How have you felt since your last visit?" All AEs (serious and nonserious) reported by the subject must be recorded on the source documents and eCRF provided by the sponsor. Adverse event collection will begin after a subject signs the ICF and assent form.

Medical terminology should be used for AE reporting. Adverse events should be reported as a single unifying diagnosis whenever possible or, in the absence of a unifying diagnosis, as individual signs or symptoms.

Exacerbation or disease progression should be reported as an AE only if there are unusual or severe clinical features that were not present, or experienced earlier, or not expected based on the course of the condition.

Protocol 405-201-00037

An AE that undergoes a change in severity, seriousness, or toxicity should be reported as a new AE on the eCRF.

In addition, the sponsor must be notified immediately by telephone, fax, or e-mail of any IREs according to the procedure outlined below, in [Section 8.8.3](#). Special attention should be paid to recording hospitalization and concomitant medications.

The AE, start date (and start time, if possible), end date (and end time, if possible), seriousness, severity, relationship to trial treatment (IMP causality), action taken with trial treatment, and outcome will be recorded on the source documents and in the eCRF.

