9.4.2.1 Adverse Events

All AEs will be coded by system organ class and Medical Dictionary for Regulatory Activities (MedDRA) preferred term. The incidence of the following events will be summarized:

- TEAEs
- TEAEs by severity
- TEAEs potentially causally related to the IMP
- TEAEs with an outcome of death
- Serious TEAEs
- TEAEs leading to discontinuation from the trial

The TEAEs will also be presented in a listing.

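### SAP 10.2 defines TEAEs more narrowly than Protocol 8.8.1, so an unchanged AE already present at dosing that makes a child leave the trial is missing from the TEAE discontinuation table

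*SAP*

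**What the plan says.** Protocol 8.8.1 defines treatment emergence in two sentences. The first is short: "Treatment-emergent AEs (TEAEs) are defined as AEs with an onset date on or after the start of open-label treatment". The second is offered as the fuller statement. It takes events that start after dosing and adds a group that was already present: "or if the event was continuous from baseline and was worsening, serious, IMP related, or resulted in death or discontinuation from the trial".

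SAP 10.2 gives its own definition: "Treatment-emergent adverse events are defined as those AEs that occur after administration of IMP or events that worsen relative to baseline". There are two routes in, new onset after dosing and worsening from baseline.

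Both documents build the discontinuation table from TEAEs. Protocol 9.4.2.1 calls it "TEAEs leading to discontinuation from the trial" and SAP 10.2 calls it "TEAEs leading to discontinuation of study". Both also tabulate related, serious and fatal TEAEs.

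Three other provisions bear on the point:
- Protocol 8.8.2, on when recording starts: "Adverse event collection will begin after a subject signs the ICF and assent form".
- Protocol 8.8.2, on events that change: "An AE that undergoes a change in severity, seriousness, or toxicity should be reported as a new AE on the eCRF".
- SAP 10.2, on listings that are not limited to TEAEs: "The listing of death due to AEs, serious AEs, AEs leading to discontinuation, and AESIs will also be provided".

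The SAP introduction states that the final SAP will be consistent with the final protocol. It does not say that the TEAE definition was changed on purpose.

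**The concern.** Tables with the same titles follow different inclusion rules in the two documents. On an ordinary reading, both SAP routes lie inside the protocol's definition, so a TEAE count made under the SAP can equal the protocol count or fall below it, but cannot exceed it. The departure therefore runs in the less cautious direction for safety reporting.

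The situation can arise. AEs are collected from consent and assent, and screening runs from Day -21 to Day -2, so a child may be dosed with an AE already on record. Protocol 7.3.3 lists discomfort from a nonserious AE as a reason to leave the trial and does not require that the AE has worsened.

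Safety and tolerability is one of the objectives listed in SAP section 2. In a trial this small, one child more or less in an incidence table is noticeable.

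**Working it through.** The plan states no figure to reproduce. The check compares the two definitions case by case, followed by one line of arithmetic.

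**Inputs.** TEAE definitions: Protocol 8.8.1 (detailed sentence) and SAP 10.2. Re-recording rule: Protocol 8.8.2. Maximum treated: 12 (Protocol 5, SAP 3.3). Analysis set: all children who receive the dose (SAP 5.2 and 10).

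**Reading the SAP sentence.** Its first route must refer to onset. If an event merely continuing after the dose counted as occurring after it, the separate route for worsening would have no purpose.

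**Cases, for an AE that began before dosing and was ongoing at dosing:**

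| Case | Protocol 8.8.1, detailed | SAP 10.2 |
|---|---|---|
| Worsened after dosing | TEAE | TEAE |
| Changed in severity, seriousness or toxicity after dosing and entered as a new AE | TEAE | TEAE, because the new record starts after dosing |
| Unchanged, led to leaving the trial | TEAE | Not a TEAE |
| Unchanged, judged related to the study drug | TEAE | Not a TEAE |
| Unchanged, already serious | TEAE | Not a TEAE |
| Resulted in death | TEAE | Captured in practice, since it will have worsened or changed in seriousness |

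The definitions differ in rows three to five. Row three feeds the discontinuation table. Protocol 7.3.2 says treatment discontinuation does not apply in a single-dose trial, so that table can only describe leaving the trial, under either title.

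**Size of one row-three case**, if all 12 are treated and no other child qualifies:
- Protocol rule: 1/12 = 8.3%.
- SAP rule: 0/12 = 0%.
- Difference: 8.3 percentage points.

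**Where that child still appears.** The SAP 10.2 listing of AEs leading to discontinuation covers all AEs. SAP 7.1 gives the number and percentage who discontinue by reason and mode of administration, and AE is one of the reasons in Protocol 7.3.3. The SAP 7.1 table uses the enrolled sample, so its denominator may differ from that of the AE tables.

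**The case against.** The best case on the other side is that the mismatch has almost no consequence.

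- **A reader might infer that any AE present at dosing which leads to discontinuation is lost.** The documents do not support this. SAP 10.2 keeps events that worsen, and Protocol 8.8.2 turns a change in severity, seriousness or toxicity into a new record. Severity is graded by effect on daily activity, so an event that becomes bad enough to make a child leave may well be graded as worse. Only an event with no recorded change is affected.
- **A reader might infer that the discontinuation goes unreported.** It does not: the SAP 10.2 listing and the SAP 7.1 table both show it. Nor is it a contradiction in itself that a listing of AEs is broader than a table of TEAEs.
- **A reader might infer a similar understatement in the related, serious and fatal tables.** These routes are close to empty. Protocol 8.8.1 defines a related AE by a reasonable possibility of a temporal and causal link, which an event that preceded the only dose and did not change afterwards can hardly meet. Children must be in good physical health to enter, so an ongoing serious AE at dosing is unlikely. A baseline event that becomes fatal has changed.
- **A reader might quote 1/6 = 16.7 points within one mode of administration.** SAP 10.2 does not state that AE incidences are tabulated by mode, whereas SAP 10.3, 10.4 and 10.6 do say so for their own data. An even split is also only an aim. That figure has no basis in the plan.
- **The protocol is not uniform.** Its short sentence rests on onset date alone and is narrower than its detailed one, so the SAP falls between the two.

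Most of this stands, and it limits the weight of the point. It does not remove the mismatch. The protocol presents the longer sentence as the detailed definition, the SAP matches neither sentence, and no reason is given. One gap has no backstop among the AE outputs named in SAP 10.2: an unchanged, nonserious baseline event judged related, which is not of special interest and does not lead to discontinuation. It would appear in no table or listing named there, though it should be very rare.

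**Conclusion.** SAP 10.2 departs, without explanation, from the detailed definition in Protocol 8.8.1, and TEAE counts under it can only be equal or lower. The practical effect is essentially confined to one table: an unchanged AE present at dosing that leads a child to leave is not counted as a TEAE leading to discontinuation. Each such child is worth 8.3 percentage points if 12 are treated, and more if fewer are.

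This rests on taking the protocol's longer sentence as its operative definition and on reading the SAP's first route as onset after dosing. The documents give no basis for estimating how often such a case would occur. With one dose, about 24 hours of assessments and a telephone call 7 (+ 2) days after dosing, it should be uncommon.

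Severity is minor. Only descriptive safety tables are involved, the child remains visible in other outputs, and Cmax, tmax and AUC0-12h are untouched.

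**What to change.** Replace the TEAE definition in SAP 10.2 with the full detailed definition from Protocol 8.8.1: AEs that start after dosing, plus events continuing from baseline that worsened, were serious, were related to the study drug, or ended in death or discontinuation from the trial. Apply the same flag to every TEAE table and to the TEAE listing, so that SAP outputs follow the protocol's definition.

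The cost is one sentence in the SAP and one derivation flag. No new data are needed, because seriousness, causality and outcome are already collected for each AE (Protocol 8.8.2) and the SAP already plans to identify AEs that lead to discontinuation. The counts may become slightly less favourable.
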